7.4.3 AEs of Special Interest

7.4.3.1 Anaphylaxis

The definition of anaphylaxis that has been adopted for this study is from the 2014 position paper by the European Academy of Allergy and Clinical Immunology (EAACI) Food Allergy and Anaphylaxis Guidelines Group (Muraro et al., 2007), that in turn was based on the publications of Simons et al. (2011) and Johansson et al. (2004), and is consistent with the recently published "International consensus on (ICON) anaphylaxis" (Simons et al., 2014). Accordingly, anaphylaxis is defined as a severe, potentially life-threatening systemic hypersensitivity reaction, characterized by being rapid in onset with life-threatening airway, breathing, or circulatory problems that is usually, though not always, associated with skin and mucosal changes.

With respect to the inclusion of being "potentially life-threatening" in the definition of anaphylaxis and how that relates to the assessment of anaphylaxis as an SAE, reference is made to the 2012 FDA Guidance for Industry and Investigators, "Safety Reporting Requirements for INDs and BA/BE Studies," that states, "An adverse event or suspected adverse reaction is considered "life-threatening" if, in the view of either the investigator or sponsor, its occurrence places the patient or subject at immediate risk of death. It does not include an adverse event or suspected adverse reaction that, had it occurred in a more severe form, might have caused death." Thus, for the reporting of anaphylaxis as an SAE, the severity of the reaction, assessed according to the EAACI system for grading the severity of anaphylactic reactions (Muraro et al., 2007), is also to be taken into account (Section 7.6 and Appendix 5).

When the diagnosis of anaphylaxis is made, the basis for having suspected the diagnosis must be documented, using the criteria established by the Second Symposium on the Definition and Management of Anaphylaxis (Sampson et al., 2006) (Appendix 3). These criteria were again affirmed in the recently published "International consensus on (ICON) anaphylaxis" (Simons et al., 2014).

7.4.3.2 Gastrointestinal Adverse Events Resulting in Prolonged Disruption of Dosing

Gastrointestinal AEs, typically chronic/recurrent GI AEs, that result in a prolonged disruption of dosing will be considered AEs of special interest and will be assessed longitudinally according to the procedures described below. For the purpose of delineating these AEs of special interest, prolonged disruption of dosing is defined as withholding study product for > 7 days. This will include 3 categories of subjects:

- Any subject whose dose is withheld for > 7 days due to GI AEs and resumes dosing at a reduced dose level (Section 6.7)
- Any subject who develops chronic/recurrent GI AEs at or before reaching the 20 mg dose level and resumes dosing after a 30-day dosing hiatus (Section 6.7.3.2);
- Any subject who permanently discontinues dosing who had experienced GI AEs (Section 4.3.2).

Subjects under the age of 18 years who fall into any of these 3 categories will be asked to fill out the PEESSTM v2.0 questionnaire (Franciosi et al., 2011), with the assistance of a parent or guardian, as appropriate, every month for 6 months; adults will be given the same questionnaire. It should, however, be noted that the PEESSTM v2.0 was not designed to establish a diagnosis of EoE, and has not been validated for use in patients with GI symptoms of other etiologies. Furthermore, the discriminant validity of the questionnaire has not been reported in either longitudinal natural history or interventional studies. For these reasons, the use of the PEESSTM v2.0 to monitor the clinical course of GI symptoms must be considered exploratory. Nevertheless, the PEESSTM v2.0 has shown good content and construct validity (Franciosi et al., 2011; Martin et al., 2015) and so holds promise for being a valuable tool to follow the clinical course of EoE or an EoE-like immune-mediated GI syndrome. Thus, the PEESSTM v2.0, could reveal trends toward symptomatic improvement or worsening that might otherwise go undetected.

Subjects who discontinue dosing prematurely due to chronic/recurrent GI AEs are to be requested to return to the clinic for evaluation monthly for at least 6 months (if the subject is asymptomatic, telephone follow-up with a physician investigator may substitute for in-clinic visit, at the investigator's discretion). If chronic/recurrent GI AEs persist beyond 6 months, subjects are to continue to be followed with monthly clinic visits until the symptoms have resolved or are assessed to have stabilized with optimal medical management.

If a subject with chronic/recurrent GI AEs has not experienced complete resolution of symptoms within 6 weeks of discontinuation of dosing with the investigational product, the subject should be referred to a (pediatric) gastroenterologist.

If a subject who discontinued dosing with the investigational product prematurely due to chronic/recurrent GI AEs is unable to discontinue the use of symptomatic therapies that may have been initiated to treat the GI AEs (eg, H1 or H2 histamine blockers or proton pump inhibitors) by 12 weeks from the time that study product was withdrawn, the subject should be referred to a (pediatric) gastroenterologist.

As is the case for any AE occurring during the study, so it is for chronic/recurrent GI AEs that the investigator may, at any time, and at his or her discretion, request consultation from an outside physician or additional testing to assist in the diagnosis or management of the AE.

If a subject is seen by a gastroenterologist, the investigational site is to procure records of the visit, as well as any test results, including those from endoscopy and endoscopic biopsy, if performed. These are to be retained with the subject's source documentation.

Subjects signing the optional consent to participate in the saliva substudy (North America sites only) will provide a saliva sample as close as possible to the time that they complete the first PEESSTM v2.0 questionnaire, and another saliva sample at the end of their post-OIT follow up period.

7.4.4 Unexpected Adverse Event

An adverse event is "unexpected" when its nature (specificity) or severity is not consistent with applicable product information, such as safety information provided in the package insert, the investigational plan, the investigator's brochure or the protocol.

7.5 Adverse Event Monitoring

7.5.1 Data Safety Monitoring Committee

Although the safety of peanut OIT overall is well established, a Data Safety Monitoring Committee (DSMC) will monitor the study for safety. The DSMC will meet periodically to review accruing safety data. The committee will consist of individuals with extensive multi-center clinical study experience drawn from the fields of clinical immunology (specifically food allergies) and biostatistics. These individuals will be entirely independent of the conduct of the study. Further details will be provided in the DSMC Charter.

7.5.2 Adjudication Committee

The Adjudication Committee (AC) will review reports of specific SAEs and AEs of special interest to verify appropriate diagnosis as per protocol definitions (eg, anaphylaxis) and appropriate determination of event seriousness, severity, and causality. The AC will provide a complete assessment of the selected cases to help independently validate these reports. Adjudication Committee assessments will be reported in addition to the investigator's assessments.

7.6 Severity Grading

The investigator is to assign severity grades to adverse events (AEs). Depending on the type of AE, different severity grading systems will be used in this study.

- The severity grading of allergic reactions will be according to the definitions developed the CoFAR group (Appendix 4).
- The severity of anaphylactic reactions will be graded according to the EAACI system for grading the severity of anaphylactic reactions (Appendix 3).
- For grading the severity of all other AEs, the National Cancer Institute's Common Terminology Criteria for Adverse Events (NCI-CTCAE) system will be used. The purpose of using the NCI-CTCAE system is to provide standard language to describe AEs ("toxicities") and to facilitate tabulation and analysis of the data and for assessment of the clinical significance of treatment-related toxicities. The NCI-CTCAE provides a term and a grade that closely describes the adverse event. Each participating site will receive copies of the grading scales and event descriptions. For additional information and a printable version of the NCI-CTCAE v. 4.03 manual, consult the NCI-CTCAE website, http://ctep.cancer.gov/reporting/ctc.html.

For adverse events not included in the NCI-CTCAE listing, they are also to be graded on a scale from 1 to 5, according to the General Grade Definition provided below:

Aimmune Therapeutics, Inc. Protocol ARC003, Amendment 4.0		CONFIDENTIAL	Page 86 of 126
Grade 1	Mild	Transient or mild discomforts (< 48 hours), no or minimal medical intervention/therapy required, hospitalization not necessary (non-prescription or single-use prescription therapy may be employed to relieve symptoms, eg, aspirin for simple headache, acetaminophen for post-surgical pain).	
Grade 2	Moderate	Mild to moderate limitation in activity, so be needed; no or minimal intervention/the hospitalization possible.	5
Grade 3	Severe	Marked limitation in activity, some assista required; medical intervention/therapy req hospitalization possible.	•
Grade 4	Life-threatening	Extreme limitation in activity, significant a significant medical/therapy intervention re hospitalization, or hospice care probable.	A -
Grade 5	Death	Death	

For additional information and a printable version of the NCI-CTCAE v. 4.03 manual, consult the NCI-CTCAE website, http://ctep.cancer.gov/reporting/ctc.html.

7.6.1 Guidelines for Determining Causality of an Adverse Event

The investigator will use the following question when assessing causality of an adverse event to study product: Is there a reasonable possibility that the study product caused the event?

An affirmative answer designates the event as a suspected adverse reaction.

7.7 Adverse Event Collection Procedures

Any new event or experience that was not present at Screening, or worsening of an event present at Screening, is considered to be an AE. Unchanged, chronic conditions are not AE's and should not be recorded on the AE page of the CRF. Adverse events will be evaluated from the onset of the event until the time the event is resolved or medically stable, or until 44 days after the subject completes study treatment, whichever comes first. Adverse events ongoing at the time that study treatment is discontinued may not be determined to be medically stable until 30 days after the Exit or Early Discontinuation Visit has been conducted, in which case additional visits after the Exit or Early Discontinuation Visit will be required. Investigators should also report AEs discovered after cessation of dosing and prior to the Early Discontinuation.

AEs may be discovered through any of these methods:

- Observing the subject
- Questioning the subject, which should be done in an objective manner
- Receiving an unsolicited complaint from the subject
- Review of medical records/source documents
- Review of home dosing symptom logs (provided to record symptoms between visits)

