6.11 Visit Windows

Dosing schedule should be adhered to strictly. Two days before, or 2 days after a planned dosing visit, is an acceptable window with continued daily dosing of the current dose level. Study visits for scheduled blood draws or DBPCFC should take place within 2 weeks of the scheduled visit.

Early Discontinuations Visits are to occur 14 days after the last dose of study product. The permissible window is minus 3 days to plus 7 days.

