- b) Subjects return to clinic every 2 weeks for up-dosing to a maximum of 300 mg, following the dose escalation schedule in Table 3-2, unless up-dosing is delayed due to allergic reaction.
- c) Any of the procedures performed at CRC Dosing Visits may be performed at Unscheduled Visits.
- d) Physical exam to include height and weight. At the investigator's discretion, symptom-directed physical exams may be completed at up-dosing visits during the Up-dosing Period, and CRC Dosing visits during the Maintenance Period. Full physical exams are to be conducted at the Screening/Baseline, the first 80 mg up-dosing, the first 300 mg up-dosing, and the Exit/Early Discontinuation (Termination) visits.
- e) Peak expiratory flow rate (PEFR): To be conducted prior to any DBPCFC, 3 attempts should be made with the best value recorded. PEFR should be measured at the same time for each visit assessment. If a subject's pulmonary status is in question at any time during the study, performance of pulmonary function testing (spirometry) is suggested.
- f) For females of childbearing potential.
- g) Blood for peanut specific IgE, IgG4 is to be drawn prior to DBPCFC.
- h) Optional blood draw for subjects \geq 30 kg only. No more than 5 mL/kg may be drawn, up to a maximum of 50 mL total; analysis by Immune Tolerance Network (ITN).
- i) Blood draw to be collected prior to the Exit DBPCFC (a second draw, 5-10 days post-DBPCFC, will be collected in ARC004; for subjects not continuing to ARC004, specimen collection should be as an Unscheduled ARC003 visit).
- j) Subjects withdrawing early from ARC003 with GI symptoms who were not already enrolled in the optional saliva substudy will be allowed to enroll upon early termination (North America sites only).
- k) Blood draw to be collected 5-10 days after the Screening DBPCFC.
- 1) Eligible subjects, those who satisfy all other screening requirements, will undergo a DBPCFC at the end of the Screening Period to a maximum challenge dose of 100 mg.
- m) Eligible subjects, those who up-dose to 300 mg and maintain for ~24 weeks, will undergo a DBPCFC at the end of Maintenance Period Visit to a maximum challenge dose of 1000 mg.
- n) AEs will be evaluated from the onset until the event is resolved or medically stable, or until 30 days after the subject completes study treatment, whichever comes first.
- o) Phone calls will occur 1 day after each escalation visit to inquire about allergic symptoms and promote compliance

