# 7.6. MISSING DATA

All AEs with partial/missing dates and times will be considered Treatment Emergent Adverse Events (TEAEs) unless a partial date clearly indicates that it occurred prior to first dose of study treatment or more than 30 days after last dose of treatment. All therapies with partial or missing dates and times recorded on the Concomitant Medication or Non-Drug Therapy CRF pages will be considered concomitant unless a partial stop date and time clearly indicates it was stopped prior to the first dose of study treatment. Start and stop dates will be imputed when partial dates are present as needed to determine treatment emergent events and concomitant medications. No imputation will be done for a completely missing start/stop date or for subjects who did not receive study treatment.

Start dates with a missing day but which have month and year populated will be imputed such that:

- If the provided month and year match the month and year for that subject's first dose date, then the Day 1 date will be used
- In all other cases the 1st of the month will be used with the provided month and year

Start dates with a missing day and month but which have year populated will be imputed such that:

- If the provided year matches the year for that subject's first dose date, then the first dose date will be used
- In all other cases the 1st of January will be used with the provided year

Stop dates will be imputed as follows:

- Missing day with a provided year and month will use the last day of the month
- Missing day and month with provided year will use December 31

If the imputed stop date is greater than the last study date for the subject, then the imputed date will be replaced with the last known subject date.

The reported date of the most recent reaction to peanut on the peanut allergy history CRF page and date of diagnosis of peanut allergy will be imputed when the month or day is missing as follows:

- Missing day is set to 1 if the same year and month as the informed consent date. Otherwise it is set to 15
- Missing month and day are set to Jan 1 if the same year as the informed consent date. Otherwise it is set to July 1.

Where the severity score of a symptom is missing during screening or exit DBPCFC, the severity score will be imputed as severe.

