## **10.3. ADVERSE EVENTS**

Symptoms that are collected during in-clinic dosing visits (including DBPCFC) are not captured on the adverse event CRF page, unless the symptom is determined to be an SAE or the subject experienced an anaphylaxis episode. Thus, each of the summaries of adverse events described below will be presented in 2 different ways:

- 1. Including only events collected on the adverse event CRF page, excluding in-clinic dosing symptoms other than SAEs and anaphylaxis episodes.
- 2. Combining adverse events collected on the adverse event CRF page and dosing symptoms collected at the in-clinic dosing visits.

All reported adverse events (AEs) will be classified into System Organ Class (SOC) and Preferred Term (PT) using Medical Dictionary for Regulatory Activities (MedDRA) version 18.1.

Treatment-emergent adverse events (TEAEs) are defined as those AEs with onset after the first dose of study drug. AEs with onset prior to first dose of study drug will be included in subject listings, but not summarized. TEAEs will be summarized for the safety population by age group (4-17 years, 4-11 years, 12-17 years, 18-55 years, and 4-55 years) and by study period as follows:

- Initial Escalation: All events beginning after the first dose of study drug on Day 1 and prior to the first at-home Up-dosing administration.
- Up-dosing: All events beginning after the first dose at-home Up-dosing administration and prior to the first at-home dose of 300 mg (which starts the Maintenance Period).
- Maintenance: All events beginning after the first dose at-home dose of 300 mg, including events after the Exit DBPCFC but prior to the rollover to ARC004.
- Overall: Across initial escalation, up-dosing, and maintenance periods.

Summaries that are displayed by system organ class and preferred terms will be ordered by descending incidence of system organ class and preferred term within each system organ class. Summaries displayed by preferred term only will be ordered by descending incidence of preferred term. Summaries of the following types will be presented:

• Overall summary of number of unique TEAEs and treatment-emergent serious adverse events (TESAEs), subject incidence of TEAEs and TESAEs meeting various criteria, and exposure adjusted incidence rates of TEAEs and TESAEs

meeting various criteria, where exposure incidence rates are defined as the total number of events divided by the total number of subject-years at risk during the study period;

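### The protocol gives two different limits for following adverse events after treatment, and the SAP's treatment-emergent rule has an end date for partially dated events only

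*Protocol*

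**What the plan says.** **Follow-up of an event.** Protocol 7.7 ends evaluation at resolution, at medical stability, or "until 44 days after the subject completes study treatment", whichever is earliest. Footnote n to Appendix 1 gives the same three end points, but the last reads "until 30 days after the subject completes study treatment, whichever comes first". Section 7.7 adds that an event ongoing when treatment stops may not be judged stable until 30 days after the Exit or Early Discontinuation Visit, and that extra visits are then needed.

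**Timing of the visit.** Protocol 6.11 states: "Early Discontinuations Visits are to occur 14 days after the last dose of study product". The permitted window is 3 days early to 7 days late.

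**Other follow-up rules for subjects who stop early.** Protocol 3.2 and 4.3.2 follow ongoing events past the Early Discontinuation Visit until they resolve or are chronic and stable, a judgement barred for the first 30 days after that visit. No outer limit is given. Protocol 7.4.3.2 has subjects who stop for chronic or recurrent GI events evaluated monthly for at least 6 months, and longer if symptoms persist.

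**Treatment-emergent status.** SAP 10.3 says treatment-emergent events "are defined as those AEs with onset after the first dose of study drug" and names no end. For events with partial or missing dates, SAP 7.6 presumes treatment-emergent status unless the partial date clearly places the event before the first dose or "more than 30 days after last dose of treatment". SAP 10.3 also defines the Maintenance Period for event summaries as "including events after the Exit DBPCFC but prior to the rollover to ARC004".

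**The concern.** There are two questions here, and they should be kept apart.

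The first is how long a known event is followed. A site working from the schedule would stop at 30 days, and a site working from the text at 44. For a subject who stopped early, either limit can expire before the protocol allows the event to be called stable, while other sections tell the same site to continue. At stake is the consistency of recorded outcome, worst grade and seriousness between sites.

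The second is which late onsets count as treatment-emergent. Completeness of the recorded date should not decide this, and under the SAP it can. The open end also matters for attribution to a study period. In SAP 10.3 the Up-dosing Period runs to the first at-home 300 mg dose, which a subject who stops during up-dosing never takes, so a fully dated event long after the last dose would still be assigned there. The exposure-adjusted rates divide events by subject-years at risk in the period. If those years are taken from the exposure periods in SAP 10.1, which end at the last dose (an assumption, since SAP 10.3 does not say), the numerator covers more time than the denominator.

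**Working it through.** **1. Follow-up limit**

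Inputs: visit 14 days after last dose, window −3 to +7 days (Protocol 6.11); 30-day wait after the visit before stability may be declared (Protocol 3.2, 4.3.2, 7.7); limits of 44 days (7.7) and 30 days (footnote n). I assume that for a subject who stops early, completing study treatment means the last dose.

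- The 44-day figure reproduces: 14 + 30 = 44.
- Gap between the two limits: 44 − 30 = 14 days.
- Visit window: 14 − 3 = day 11 to 14 + 7 = day 21.
- Earliest permitted stability date: 11 + 30 = day 41 to 21 + 30 = day 51.
- The 30-day limit always falls short, by 41 − 30 = 11 to 51 − 30 = 21 days.
- The 44-day limit falls short whenever the visit is after day 14. A visit on day 15 to 21 gives a stability date of day 45 to 51, up to 51 − 44 = 7 days past the limit.
- For completers, if the Exit Visit coincides with the last dose (assumption), the stability date is 0 + 30 = day 30 and footnote n just fits. But footnote n is not limited to completers.

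**2. Treatment-emergent status by onset day**

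| Onset after last dose | Fully dated (SAP 10.3) | Partial date clearly showing more than 30 days (SAP 7.6) |
|---|---|---|
| Day 1–30 | Treatment-emergent | Not applicable |
| Day 31 onward | Treatment-emergent | Not treatment-emergent |

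Example: last dose 1 March. An event dated 10 April is on day 40 and is treatment-emergent. An event recorded only as April began on 1 April at the earliest, which is day 31, so it is excluded even if it also began on 10 April.

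**3. How often a month-only date triggers the exclusion**

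If the last dose is on day *d* of a month with *L* days, the first of the next month is *L* − *d* + 1 days later. That exceeds 30 only if *d* < *L* − 29, so only for *d* = 1 in a 31-day month. In general the recorded month must be a later one. With a last dose on 15 March, an event recorded as April could have begun on day 31 − 15 + 1 = 17 and is kept. One recorded as May began no earlier than day 17 + 30 = 47 and is excluded, whereas the same event dated 1 May in full is kept. The mismatch is real but needs a late onset as well as an incomplete date.

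**4. Who is exposed to the open end**

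For subjects who roll over to ARC004, period attribution stops at rollover. It does not stop for subjects who discontinue early or who are not eligible to roll over.

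**The case against.** The strongest reply is that little is lost in practice.

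- *Follow-up is protected elsewhere.* Protocol 3.2 and 4.3.2 follow ongoing events in early discontinuers without a cap, and 7.4.3.2 gives those who stop for chronic or recurrent GI events at least 6 months. A reader might infer that the 30-day footnote loses outcome data mainly in AR101 subjects, including possible eosinophilic esophagitis. The documents do not support that: this is the group with the longest follow-up. The reply stands against the inference. It does not remove the contradiction, because those sections conflict with both limits.
- *The 44- and 30-day limits do not select events.* They say how long an event is evaluated after onset, so a reader who infers that they change event counts goes too far. Counts would move only if a site or programmer used a limit as a collection window. This stands.
- *Late events may be few.* Protocol 7.7 asks for newly discovered events only up to the Early Discontinuation Visit, and the SAP mismatch also needs an incomplete date. This stands as a limit on size. Late events can still enter the database, for example during the 6-month GI follow-up.
- *ARC001 gives no count.* Scaling its 6 of 29 early withdrawals to this trial's AR101 arm would project all early discontinuers, not those with a late or still unresolved event.

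**Conclusion.** Both inconsistencies are in the current text, and I found nothing in either document that resolves them.

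The follow-up limits differ by 14 days. For early discontinuers the 30-day limit precedes the earliest permitted stability date by 11 to 21 days, and the 44-day limit can precede it by up to 7. It is tempting to conclude that 44 days is the only compatible figure because 14 + 30 = 44. That holds only when the visit is on or before day 14, and the permitted window runs to day 21. The consequence is for recorded outcome, worst grade and seriousness.

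In the SAP, treatment-emergent status for onsets more than 30 days after the last dose can depend on date completeness. This is the part that bears directly on counts, mainly in early discontinuers. The number of events affected cannot be derived from the documents and is probably small.

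The day counts assume that completing study treatment and taking the last dose are the same date for these subjects. Efficacy analyses, sample size and power are unaffected. This is a consistency correction, worth making because it costs almost nothing.

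**What to change.** **Protocol.** Reconcile 7.7, footnote n of Appendix 1, 3.2, 4.3.2 and 7.4.3.2 into one follow-up rule that fits the requirement of visit plus 30 days, including the visit window in 6.11. State whether any outer limit applies to subjects who stop early. The choice of limit is the sponsor's; the passages only have to agree.

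**SAP.** State one end to the treatment-emergent period in 10.3, including how rollover to ARC004 bounds it, and apply it in 7.6 to full and partial dates alike: a partially dated event is excluded only if the earliest onset its date allows is past that same end. This end need not equal the follow-up limit, since one governs onset and the other duration of evaluation. Events beginning later, such as during the 6-month GI follow-up, can be listed separately. Say in 10.3 where subject-years at risk end, so that exposure-adjusted rates use the same period above and below the line.

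**Cost.** Wording in the protocol text, one footnote and two SAP sections. SAP 6.5 already provides for documenting such changes before database lock. No new data collection follows from the SAP change.
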